5.5.2 Disease Progression

It is anticipated that a proportion of subjects will experience disease progression. Disease progression should not be reported as an AE. Clinical signs and symptoms due to disease progression will be collected as AEs. Individual signs and symptoms will be listed rather than the term “disease progression” with the following exception: if disease progression is the cause of death, this event may be recorded as an AE with “disease progression” as the reported term.

5.5.3 Definition of Serious Adverse Events (SAEs)

An adverse event is considered “serious” if, in the view of either the investigator or sponsor, it results in any of the following outcomes:

- Results in death
- Is life threatening (an event is considered “life-threatening” if, in the view of either the investigator or sponsor, its occurrence places the subject at immediate risk of death. It does not include an adverse event that, had it occurred in a more severe form, might have caused death)
- Results in persistent or significant disability/incapacity or substantial disruption of the ability to conduct normal life functions
- Results in congenital anomaly, or birth defect
- Requires inpatient hospitalization or leads to prolongation of hospitalization (hospitalization for treatment/observation/examination caused by AE is to be considered as serious)
- Other medically important events.

Medical and scientific judgment should be exercised in deciding whether expedited reporting is appropriate in other situations, such as important medical events that may not be immediately life-threatening or result in death or hospitalization but may jeopardize the subject or may require intervention to prevent one of the other outcomes listed in the definition above. These events, including those that may result in disability/incapacity, should also usually be considered serious. Examples of such events are intensive treatment in an emergency room or at home for allergic bronchospasm; blood dyscrasias or convulsions that do not result in hospitalization; or development of drug dependency or drug abuse.

Safety events of interest on a Sponsor medicinal product that may require expedited reporting and/or safety evaluation include, but are not limited to:

- Overdose of a Sponsor medicinal product
- Suspected abuse/misuse of a Sponsor medicinal product
- Inadvertent or accidental exposure to a Sponsor medicinal product
- Medication error involving a Sponsor product (with or without subject exposure to the Sponsor medicinal product, e.g., name confusion)

All of the events of interest noted above should be recorded on the eCRF. Any situation involving these events of interest that also meets the criteria for an SAE should be recorded on the AE page of the eCRF and marked 'serious' and the SAE worksheet.

The Sponsor has a list of events that they classify as 'always serious' events. If an adverse event is reported that is considered to be an event per this classification as 'always serious', additional information on the event may be requested.

5.5.4 Criteria for Causal Relationship to the Study Drug

Adverse events that fall under either "Possible" or "Probable" should be defined as "AEs whose relationship to the study drugs could not be ruled out". The following table describes the criteria for determining causal relationship of AEs.

Table 3 Criteria for Causal Relationship

Causal relationship to the study drug	Criteria for casual relationship
Not Related	A clinical event, including laboratory test abnormality, with a temporal relationship to drug administration, which makes a causal relationship improbable, and/or in which other drugs, chemicals or underlying disease provide plausible explanations.
Possible	A clinical event, including laboratory test abnormality, with a reasonable time sequence to administration of the drug, but which could also be explained by concurrent disease or other drugs or chemicals. Information on drug withdrawal may be lacking or unclear.
Probable	A clinical event, including laboratory test abnormality, with a reasonable time sequence to administration of the drug, unlikely to be attributed to concurrent disease or other drugs or chemicals, and which follows a clinically reasonable response on re- administration (rechallenge) or withdrawal (dechallenge).

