5.5.9 Procedure in Case of Pregnancy

If during the conduct of the clinical trial, a male subject impregnates his partner, the subject should report the pregnancy to the investigator. The investigator should report the pregnancy to the sponsor as an SAE within 30 days from discontinuation of dosing. The expected date of delivery or expected date of the end of the pregnancy, last menstruation, estimated fertility date, pregnancy result and neonatal data etc., should be included in this information.

The investigator will follow the medical status of the mother, as well as the fetus, as if the pregnancy is an SAE and will report the outcome to the sponsor.

When the outcome of the pregnancy falls under the criteria for SAEs [spontaneous abortion, induced abortion, stillbirth, death of newborn, congenital anomaly (including anomaly in a miscarried fetus)], the investigator should respond in accordance with the report procedure for SAEs. Additional information regarding the outcome of a pregnancy (which is categorized as an SAE) is mentioned below.

- "Spontaneous abortion" includes abortion and missed abortion.
- Death of an infant within 1 month after birth should be reported as an SAE regardless of its relationship with the study drug.
- If an infant dies more than 1 month after the birth, it should be reported if a relationship between the death and intrauterine exposure to the study drug is judged as "possible" by the investigator.
- In the case of a delivery of a living newborn, the "normality" of the infant is evaluated at the birth.
- "Normality" of the miscarried fetus is evaluated by visual examination unless test results which indicate a congenital anomaly are obtained prior to miscarriage.

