7.5.1 Adverse Events

AEs will be coded to system organ class and preferred term using the Medical Dictionary for Regulatory Authorities (MedDRA) and graded using NCI-CTCAE.

Treatment-emergent adverse events (TEAE) will be presented within each system organ class by preferred term, by relationship to study drug and by severity (NCI-CTCAE grade). AEs leading to dose reduction or temporary discontinuation of study drug, AEs leading to permanent discontinuation of study drug, SAEs, and SAEs by NCI-CTCAE grade will be summarized. AEs will also be summarized by NCI-CTCAE grade and relationship to study drug jointly.

All AEs data will be displayed in listings. In addition listings of deaths, SAEs, drug related AEs, AEs leading to dose reduction or temporary discontinuation of study drug and AEs leading to permanent discontinuation of study drug will be presented.

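### The causality categories in protocol Table 3 overlap across the related/not-related line and leave a gap, so the wording does not determine which AEs count as drug-related

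*Protocol*

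**What the plan says.** Protocol 5.5.4, Table 3, has three rows.

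- *Not Related*: an event whose timing is one "which makes a causal relationship improbable, and/or in which other drugs, chemicals or underlying disease provide plausible explanations".
- *Possible*: an event "with a reasonable time sequence to administration of the drug, but which could also be explained by concurrent disease or other drugs or chemicals". The row adds: "Information on drug withdrawal may be lacking or unclear".
- *Probable*: an event with reasonable timing that is "unlikely to be attributed to concurrent disease or other drugs or chemicals, and which follows a clinically reasonable response on" rechallenge or withdrawal.

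The sentence above the table says that *Possible* and *Probable* events "should be defined as 'AEs whose relationship to the study drugs could not be ruled out". It names the group once a row has been chosen and does not help to choose the row.

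The codes are used in several places. SAP 6.2 lists relationship as one dimension of the TEAE variable. Protocol 7.5.1 and SAP 7.5.1 present TEAEs by relationship, and the SAP states: "AEs will also be summarized by NCI-CTCAE grade and relationship to study drug jointly". SAP 7.5.1 also promises a drug-related listing ("In addition listings of deaths, SAEs, drug related AEs") but does not say which codes are drug-related. Protocol 5.5.6 makes causality part of the minimum data for every SAE report. Protocol 5.5.9 makes an infant death more than one month after birth reportable when a link between the death and "intrauterine exposure to the study drug is judged as 'possible' by the investigator".

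**The concern.** A causality scale should place each event in exactly one category. Table 3 does not. The and/or lets either limb satisfy *Not Related*, so a plausible disease explanation is enough even when timing fits the drug, and those same two facts define *Possible*. The two rows fall on opposite sides of the related/not-related split, so the ambiguity reaches the drug-related count and not only its subdivision.

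This is a practical problem in this population. Protocol 1.3 lists asthenia/fatigue, back pain, hematuria and spinal cord compression among the common adverse drug reactions. Appendix 3 lists the same four among SAEs expected in these subjects, and 5.5.8 describes that list as independent of drug exposure. Section 5.5.2 has signs and symptoms of progression recorded as AEs. Subjects enter without a break in dosing (3.2), so timing will seldom rule the drug out.

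The gap is also practical. Dosing continues by default (5.1.1). Interruption for toxicity is described only for events of grade 3 or more that medical treatment cannot relieve (5.1.2). A milder event with no other apparent cause will often have no dechallenge information.

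There is no comparator (4.1.2), so no control rate stands beside the relationship tables.

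**Working it through.** The plan states no figure to reproduce. The check is whether the three rows are mutually exclusive and exhaustive.

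**Inputs.** All three come from Table 3: timing (reasonable, or making causation improbable), alternative explanation (plausible or unlikely), and dechallenge/rechallenge (positive, lacking or unclear, negative). This gives 2 × 2 × 3 = 12 combinations.

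**Rows as conditions.**
- *Not Related*: improbable timing OR plausible alternative.
- *Possible*: reasonable timing AND plausible alternative. The remark on withdrawal information is permissive and does not remove the need for an alternative.
- *Probable*: reasonable timing AND alternative unlikely AND positive response.

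Column A is the text as written. Column B reads and/or strictly as 'and'. Column C is B with *Possible* widened to take events with no alternative and no dechallenge information.

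| Timing | Alternative | De-/rechallenge | Cells | A | B | C |
|---|---|---|---|---|---|---|
| reasonable | plausible | any | 3 | Not Related and Possible | Possible | Possible |
| reasonable | unlikely | positive | 1 | Probable | Probable | Probable |
| reasonable | unlikely | lacking/unclear | 1 | none | none | Possible |
| reasonable | unlikely | negative | 1 | none | none | none |
| improbable | plausible | any | 3 | Not Related | Not Related | Not Related |
| improbable | unlikely | any | 3 | Not Related | none | none |

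- A: 3 cells meet two rows, 1 + 1 = 2 meet none, and 12 − 3 − 2 = 7 meet exactly one.
- B: 0 meet two rows and 1 + 1 + 3 = 5 meet none.
- C: 0 meet two rows and 1 + 3 = 4 meet none.

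Replacing and/or with 'and' therefore removes the overlap but raises the uncovered cells from 2 to 5. Widening *Possible* for absent dechallenge brings that back only to 4. *Possible* and *Probable* never overlap.

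**Effect on counts.** Let r be the share of AEs that are related on any reading and q the share in the overlap. The related share can lie anywhere from r to r + q with every coding compliant, so the possible difference is q. The documents give no AE frequencies. For assumed q of 10%, 30% and 50%, the difference is up to 10, 30 and 50 per 100 AEs. The cells are logical cases without weights, so 3 of 12 does not mean a quarter of events.

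The gap behaves differently. It moves the related count only if such an event is left uncoded or forced into *Not Related*. Placed in *Possible* or *Probable*, it changes only the split between those two.

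**Check of the rewording proposed under the fix.** Split the alternative into three levels: strong enough to make a drug contribution unlikely, plausible but weaker, and unlikely. That gives 2 × 3 × 3 = 18 cells. Improbable timing gives 9 *Not Related*. Reasonable timing with a strong alternative gives 3 *Not Related*. Reasonable timing with a weaker alternative gives 3 *Possible*. Reasonable timing with the alternative unlikely gives 1 *Probable* (positive response) and 2 *Possible*. The total is 9 + 3 + 3 + 1 + 2 = 18, with one row per cell.

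**The case against.** The strongest reply is that little of the safety reporting depends on this code. The study is descriptive, with no inferential analysis. TEAEs by system organ class, preferred term and grade, SAEs, and AEs leading to discontinuation are summarised whatever the causality, and all AEs are listed. Investigators report SAEs regardless of relationship. The primary endpoint in protocol 2.3.1 does not mention relationship, although SAP 6.2 does. All of this stands, and it limits the severity.

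It can also be said that an investigator would naturally put an event without dechallenge into *Possible*, given that row's remark on withdrawal information, and that the lead sentence steers away from *Not Related*. This is a sensible reading and makes the gap less harmful, but it is not what the row requires, and it does nothing for the overlap.

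On 5.5.9, 'possible' can be read as a minimum that includes 'probable', and the section already has pregnancies followed as if they were SAEs, with outcomes reported. The omission is a drafting slip that affects no AE table.

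A reader might infer that the drug-related rate is biased downward, since most events in cancer patients have a disease explanation. The documents do not show how sites would code such events, so no direction follows. A reader might also construct a swing in the related share from, say, 10% to somewhere between 50% and 90%. Those figures rest wholly on assumed shares and on all sites taking the same extreme reading. They also count events with no alternative cause as related, when Table 3 often gives such events no row.

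**Conclusion.** Table 3 is neither mutually exclusive nor exhaustive, and nothing in the protocol or SAP sets an order of precedence. The relationship tables, the drug-related AE listing and the SAE causality field can differ between compliant sites by up to the whole share of overlapping events. The overlap and the gap follow from the wording alone. The size of the effect depends on a share that the documents do not give, and its direction depends on site behaviour that they do not describe. All-causality outputs are unaffected and no hypothesis test is involved.

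Severity is moderate. A reader might infer that the plan cannot go forward without the change. For a descriptive study that is being closed, with full all-causality reporting, the documents do not support that.

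**What to change.** **Protocol Table 3.** Do not simply change and/or to 'and'.

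- *Not Related*: timing makes causation improbable; or timing is reasonable and an alternative explanation is strong enough to make a drug contribution unlikely.
- *Possible*: every other event with reasonable timing that does not meet *Probable*, including events with no alternative cause and no dechallenge information.
- *Probable*: unchanged.

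**Protocol 5.5.9.** Write 'possible or probable'.

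**SAP 7.5.1.** Define drug-related as *Possible*, *Probable* or missing relationship. The SAP has no rule for a missing code, and the general no-imputation principle in 7.9.1 would leave such an event outside the related counts. This is a separate omission, but it matters here because an event that fits no row may be left blank.

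**Cost.** The work is a protocol wording change, an eCRF completion note and a sentence in the SAP, which is finalised before hard lock. Drug-related counts may become less favourable. AEs coded before the change were judged under the old table, so the database would mix two definitions unless those events are reassessed, and the report should say so. The SAP and 5.5.9 changes need no recoding and can be made even if Table 3 is left as it is because the study is closing.

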5.5.5 Criteria for Defining the Severity of an Adverse Event

Severity of AEs will be graded according to the Common Terminology Criteria for Adverse Events (CTCAE) v. 4.0 of the National Cancer Institute (NCI) Cancer Therapy Evaluation Program (CTEP). For terms not specified within NCI-CTCAE, the following guideline should be used to determine grade as below in [Table 4](#)

Table 4 Criteria for Severity of Adverse Event Terms Not Specified Within NCI-CTCAE

Grade	Description
1	Mild; asymptomatic or mild symptoms, clinical or diagnostic observations only; intervention not indicated
2	Moderate; minimal, local or noninvasive intervention indicated; limiting age-appropriate instrumental activities of daily living
3	Severe or medically significant but not immediately life-threatening; hospitalization or prolongation or hospitalization indicated; disabling; limiting self care activities of daily living
4	Life-threatening consequences; urgent intervention indicated
5	Death related to AE

5.5.6 Reporting of Serious Adverse Events (SAEs)

In the case of a serious adverse event (SAE), the investigator must contact the Sponsor by telephone or fax immediately (within 24 hours of awareness). The investigator should complete and submit a report/report form containing all information that is required by the Regulatory Authorities to the Sponsor by fax immediately (within 24 hours of awareness). If the faxing of the report/report form or an SAE Worksheet is not possible or is not possible within 24 hours, the 24h contact for SAEs should be informed by phone. For contact details, see Section [II](#) Contact Details of Key Sponsor's Personnel.

Please email or fax the SAE Worksheet to:

Astellas Pharma Global Development,
Product Safety and Pharmacovigilance

Fax number: [REDACTED]

Email: [REDACTED]

If there are any questions, or if clarification is needed regarding the SAE, please contact the Sponsor's Medical Director/Expert or his/her designee (see Section [II](#) Contact Details of Key Sponsor's Personnel).

Follow-up information for the event should be sent promptly (within 7 days) as necessary.

The sponsor or sponsor's designee will submit expedited safety reports (i.e. IND Safety Reports) to the regulatory agencies (i.e. FDA) as necessary, and will inform the investigators of such regulatory reports. Investigators must submit safety reports as required by their Institutional Review Board (IRB)/Independent Ethics Committee (IEC) within timelines set by regional regulations (i.e. EU, (e) CTD, FDA). Documentation of the submission to and receipt by the IRB/IEC of expedited safety reports should be retained by the site.

You may contact the sponsor's Medical Director/Expert for any other problem related to the safety, welfare, or rights of the study participant (subject/patient).

Full details of the SAE should also be recorded on the medical records and on the eCRF

The following minimum information is required:

- ISN/Study number
- Subject number, sex and age
- The date of report
- A description of the SAE (event, seriousness of the event)
- Causal relationship to the study drug.

SAEs will be collected from the time of study drug administration on Day 1 through 30 days after the last dose of study drug.

The Sponsor will notify all investigators responsible for ongoing clinical studies with the study drug of all SAEs which require submission to their IRB/IEC within timelines set by regional/country regulations.

The investigators should provide written documentation of IRB/IEC notification for each report to the Sponsor.

For Suspected Unexpected Serious Adverse Reactions (SUSAR) from a blinded trial, unblinded CIOMS-I report will be submitted to the authorities and IRB/IEC where required.

All SAEs recorded up to 30 days after the last study drug intake should be reported, i.e. even if they occur after the end of study visit.

5.5.7 Follow-up to Adverse Events

All adverse events occurring during treatment are to be followed up until resolved or judged to be no longer clinically significant, or until they become chronic to the extent that they can be fully characterized (all follow-up results are to be reported to the sponsor or delegated CRO).

For those subjects that transition to Study [REDACTED], it is not needed to collect AEs and SAEs after the last dose within this study, as these will be collected as part of the extension study.

For subjects who do not transition to Study [REDACTED], any adverse event that progresses to an “SAE” or if a subject experiences a new SAE, the investigator must immediately report the information to the sponsor.

Please refer to [Appendix 2](#) (Liver Safety Monitoring and Assessment) for detailed instructions on DILI follow-up responsibilities related to history of symptoms, concomitant drug use, alcohol use, and recreational drug use.

5.5.8 Monitoring of Common Serious Adverse Events

Included in [Appendix 3](#) (Common Serious Adverse Events) is a list of SAEs commonly anticipated to occur in the study population independent of drug exposure that will be monitored by the Sponsor throughout the course of the study for any change in frequency.

Any changes to this list will be communicated to the participating investigational sites. Investigators must report individual occurrences of these events [Section 0].

5.5.9 Procedure in Case of Pregnancy

If during the conduct of the clinical trial, a male subject impregnates his partner, the subject should report the pregnancy to the investigator. The investigator should report the pregnancy to the sponsor as an SAE within 30 days from discontinuation of dosing. The expected date of delivery or expected date of the end of the pregnancy, last menstruation, estimated fertility date, pregnancy result and neonatal data etc., should be included in this information.

The investigator will follow the medical status of the mother, as well as the fetus, as if the pregnancy is an SAE and will report the outcome to the sponsor.

When the outcome of the pregnancy falls under the criteria for SAEs [spontaneous abortion, induced abortion, stillbirth, death of newborn, congenital anomaly (including anomaly in a miscarried fetus)], the investigator should respond in accordance with the report procedure for SAEs. Additional information regarding the outcome of a pregnancy (which is categorized as an SAE) is mentioned below.

- "Spontaneous abortion" includes abortion and missed abortion.
- Death of an infant within 1 month after birth should be reported as an SAE regardless of its relationship with the study drug.
- If an infant dies more than 1 month after the birth, it should be reported if a relationship between the death and intrauterine exposure to the study drug is judged as "possible" by the investigator.
- In the case of a delivery of a living newborn, the "normality" of the infant is evaluated at the birth.
- "Normality" of the miscarried fetus is evaluated by visual examination unless test results which indicate a congenital anomaly are obtained prior to miscarriage.

5.5.10 Supply of New Information Affecting the Conduct of the Study

When new information becomes available, including "Dear Doctor Letters" but not limited to that, necessary for conducting the clinical study properly will lead to a protocol amendment, the sponsor should inform regulatory authorities, as well as all investigators involved in the clinical study, who will then inform the IRB/IEC of such information, and when needed, should amend the subject information.

